2. LIST OF ABBREVIATIONS

Include a list of all abbreviations used in the TSAP

| Term | Definition / description |
|-------------------|--|
| AE | Adverse Event |
| AESI | Adverse Events of Special Interest |
| ALT | Alanine Aminotransferase (or SGPT) |
| ANCOVA | Analysis of Covariance |
| ANTE(1) | First-order Ante-dependence |
| AR(1) | First-order Autoregressive |
| ARH(1) | Heterogeneous First-order Autoregressive |
| AST | Aspartate Aminotransferase (or SGOT) |
| AUC | Area Under the Curve |
| BIcMQ | Boehringer Ingelheim Customised MedDRA Query |
| BMI | Body Mass Index |
| BRPM | Blinded Report Planning Meeting |
| CEC | Clinical Event Committee |
| CTC | Common Terminology Criteria |
| CTP | Clinical Trial Protocol |
| CTR | Clinical Trial Report |
| DBL | Database Lock |
| DM&SM | Boehringer Ingelheim Data Management and Statistics Manual |
| DMG | Dictionary Maintenance Group |
| DI | Disposition Index |
| DRA | Drug Regulatory Affairs |
| ECG | Electrocardiogram |
| eCRF | Electronic Case Report Form |
| EMA | European Agency for the Evaluation of Medicinal Products |
| EoT | End-of-Trial |
| FAS | Full Analysis Set |
| FPG | Fasting Plasma Glucose |
| FPI | Fasting Plasma Insulin |
| GFR | Glomerular Filtration Rate |
| HbA _{1c} | Glycosylated Haemoglobin A1c |

16.1.9 Documentation of statistical methods

Proprietary confidential information © 2019 Boehringer Ingelheim International GmbH or one or more of its affiliated companies

Proprietary confidential information © 2019 Boehringer Ingelheim International GmbH or one or more of its affiliated companies

| Term | Definition / description |
|--------|--|
| ICH | International Conference on Harmonisation |
| ITT | Intention-to-treat |
| IRT | Interactive Response Technology |
| LOCF | Last Observation Carried Forward |
| MedDRA | Medical Dictionary for Regulatory Activities |
| MMRM | Mixed Model Repeated Measures |
| MQRM | Medical Quality Review Meeting |
| MTT | Meal Tolerance Test |
| NCF | Non-Completers Considered as Failure |
| O*C | Oracle Clinical |
| OC | Observed Cases |
| PK | Pharmacokinetics |
| PPG | Post-prandial Glucose |
| PPS | Per Protocol Set |
| PSTAT | Project Statistician |
| PT | Preferred Term |
| PV | Protocol Violation |
| Q1 | Lower Quartile |
| Q3 | Upper Quartile |
| REML | Restricted Maximum Likelihood |
| REP | Residual Effect Period |
| RS | Randomised Set |

3. INTRODUCTION

As per International Conference on Harmonisation (ICH) E9, the purpose of this document is to provide a more technical and detailed elaboration of the principal features of the analysis described in the protocol, and to include detailed procedures for executing the statistical analysis of the primary and secondary variables and other data.

This trial statistical analysis plan (TSAP) assumes familiarity with the Clinical Trial Protocol (CTP), including Protocol amendments. In particular, the TSAP is based on the planned analysis specification as written in CTP Section 7 “Statistical Methods and Determination of sample size”. Therefore, TSAP readers may consult the CTP for more background information on the study, e.g., on study objectives, study design and population, treatments, definition of measurements and variables, planning of sample size, and randomization.

SAS[®] Version 9.4 or later version will be used for all analysis.

4. CHANGES IN THE PLANNED ANALYSIS OF THE STUDY

Due to an alignment of terminology and analysis of hypoglycaemic events on project level, the new definition and analyses were applied in the TSAP, including investigator defined hypoglycaemic AE and severe hypoglycaemic AE.

The definitions of treated set and full analysis set were updated to be more accurate.

| Text in CTP | Adjusted text in TSAP |
|--|--|
| TS - Treated Set The treated set (TS) will consist of all patients who were randomised and treated with at least one dose of study drug. | TS - Treated Set It consists of all patients treated with at least one dose of study drug. The TS is the basis for safety analyses. |
| FAS - Full Analysis Set The full analysis set (FAS) will consist of all patients in the TS who had a baseline HbA _{1c} value and at least one on-treatment HbA _{1c} value. | FAS - Full Analysis Set It consists of all patients randomised in the TS who had a baseline HbA _{1c} value and at least one on-treatment HbA _{1c} value. The FAS is the basis for the intention-to-treat (ITT) analysis. |

5. ENDPOINT(S)

5.1 PRIMARY ENDPOINT(S)

The primary endpoint in this study is the change from baseline in HbA_{1c} after 24 weeks of treatment (HbA_{1c} after 24 weeks of treatment minus HbA_{1c} at baseline), where “baseline” refers to the last observation prior to the start of randomised study drug, including the observation prior to the placebo run-in. HbA_{1c} will be measured in the unit of % at all clinical visits. No transformation (e.g. logarithmic) of the change from baseline in HbA_{1c} values will be done.

5.2 SECONDARY ENDPOINT(S)

5.2.1 Key secondary endpoint(s)

Not applicable in this trial.

5.2.2 (Other) Secondary endpoint(s)

Secondary efficacy endpoints are:

- Change from baseline in FPG after 24 weeks of treatment
- Change from baseline in 2-hour PPG after 24 weeks of treatment
- Proportion of patients with HbA_{1c} on treatment <7.0% after 24 weeks of treatment
- Proportion of patients with HbA_{1c} on treatment <6.5% after 24 weeks of treatment
- Proportion of patients with HbA_{1c} lowering by at least 0.5% after 24 weeks of treatment

The secondary safety endpoints defined in CTP regarding investigator defined hypoglycaemic AE and severe hypoglycaemic AE were included in [Section 7.8](#) Safety Analyses.

6. GENERAL ANALYSIS DEFINITIONS

6.1 TREATMENT(S)

There will be 5 treatment phases in this trial: screening period, placebo run-in period, double-blind treatment period (with either BI drug or matching placebo), post-treatment and post-study.

Table 6.1: 1 Treatment regimens / study intervals

| Label | Interval | Start date | Start time |
|------------------------|----------------------------------|--|---|
| Screening | Screening period | Date of informed consent | 00:00 |
| Run-in Placebo | Placebo run-in period | Date of first administration of run-in medication | 00:00 |
| Lina 5 mg / Placebo | Double-blind treatment period | Date of first administration of study medication for double-blind treatment period | Time of first administration of study medication, 12:00 if missing |
| Post-treatment | Post-treatment | Date of last drug intake + X* + 1 | 00:00 |
| Post-study | Post-study | Date of last contact + 1 | 00:00 |

* The endpoint specific follow-up period for the assignment to active treatment are presented in detail in [Section 6.7](#).

The purpose of the definition in the above is to describe all the different study/treatment intervals, in which a patient can lie during the course of the trial. Note that the term “treatment regimen” can also cover time periods with no active treatment.

The efficacy and safety analyses will follow the intention-to-treat (ITT) principle in assigning patients to treatment groups, i.e. patients will be analysed as randomised.

If a patient erroneously receives the wrong trial drug, the patient will be analysed ‘as randomised’. Additionally, the AEs with an onset during the time of the incorrect study treatment will also be listed separately.

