7.3.4 Safety analyses

Safety analysis will be performed on TS, with patients assigned to the treatment they were randomised. In general, safety analyses will be descriptive in nature and will be based on BI standards. No hypothesis testing is planned.

Statistical analysis and reporting of AEs will concentrate on treatment-emergent AEs. To this end, all AEs occurring between start of treatment and end of REP will be considered 'treatment-emergent'. The REP is defined as a period of seven days after the last dose of trial medication. AEs that start before first drug intake and deteriorate under treatment will also be considered as 'treatment-emergent'. Frequency, severity, and causal relationship of AEs will be tabulated by system organ class and preferred term after coding according to the current version of the Medical Dictionary for Drug Regulatory Activities (MedDRA).

Laboratory data will be analysed both quantitatively as well as qualitatively. The latter will be done via comparison of laboratory data to their reference ranges. Values outside the reference range as well as values defined as clinically relevant will be highlighted in the listings. Treatment groups will be compared descriptively with regard to distribution parameters as well as with regard to frequency and percentage of patients with abnormal values or clinically relevant abnormal values.

Vital signs, physical examinations, or other safety-relevant data observed at screening, baseline, during the course of the trial and at the end-of-trial evaluation will be assessed with regard to possible changes compared to findings before start of treatment.

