16.1.9 Documentation of statistical methods

Proprietary confidential information © 2019 Boehringer Ingelheim International GmbH or one or more of its affiliated companies

Boehringer Ingelheim

TSAP for BI Trial No: 1218.102

Proprietary confidential information © 2019 Boehringer Ingelheim International GmbH or one or more of its affiliated companies

Table 6.2: 1 (continued) Important protocol violations

| PV Category / Code | Description | Criterion to check for PV (Comments) | Efficacy (E) or Safety (S) | PV Leading to Exclusion from PPS |
|--------------------|---|---|----------------------------|----------------------------------|
| B | Informed consent | | | |
| B1 | Informed consent not available | Date of informed consent missing Or No signature on patient's "Declaration of Informed Consent" Patient's data will not be used at all. | S/E | Yes |
| B2 | Informed consent too late | Date of informed consent not obtained prior to any study related procedure or re-consent with new version of informed consent too late. Minimum requirement for initial informed consent <= date of Visit 1/date of any study procedure | S | No |
| C | Trial medication and randomisation | | | |
| C1 | Incorrect trial medication taken | | | |
| C1.1 | No study medication taken | Patient randomised but no study medication taken. Exclude also from FAS and TS. | E | Yes |
| C1.2 | Incorrect trial medication taken | Wrong medication taken (different medication than the patient was randomised to taken at any visit, i.e. drug kit recorded in eCRF from different treatment group than drug kit assigned by IVRS) Can only be finally judged after DBL since unblinding information is required. | E | Yes |
| C2 | Randomisation not followed | | | |
| C2.1 | Treated without randomisation | Patient treated according to eCRF but not randomised by IVRS. Exclude also from FAS and RS. | E | Yes |
| C3 | Non-compliance | | | |
| C3.1 | Non-compliance with drug intake | Gross non-compliance issues only – based on compliance section of CRF (at least two times on treatment compliance was outside 80-120% according to eCRF) Final decision at the DBL meeting. (medical judgement) | E | Yes |

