6.3 PATIENT SETS ANALYSED

SCR - Screened Patients Set

It consists of all patients screened for the trial, with informed consent given and who completed at least some screening procedures at Visit 1.

RS - Randomised set

It consists of all patients from the screened set who were randomised to study drug, regardless of whether any study drug was taken.

TS - Treated Set

It consists of all patients treated with at least one dose of study drug. The TS is the basis for safety analyses.

FAS - Full Analysis Set

It consists of all patients randomised in the TS who had a baseline HbA1c value and at least one on-treatment HbA1c value. The FAS is the basis for the intention-to-treat (ITT) analysis.

FAS - Completers

It consists of all patients in the FAS with treatment duration no less than 149 days and did not prematurely discontinue the trial. The date of last intake of study drug should be on or after the start of the time window of the last on-treatment visit, and an HbA1c value should be available within the time window for this visit.

PPS - Per Protocol Set

It consists all patients in the FAS without important PVs for efficacy.

MTT-set - Meal Tolerance Test set

It consists all patients of the FAS with a valid MTT at baseline and at the end of the study. An MTT is considered valid if it has a valid FPG and a valid 2 hour PPG value.

Table 6.3: 1 Check-box for data set to be used for which class of endpoints

| Class of endpoint | TS | FAS | MTT-set |
|--|----|-----|---------|
| Primary endpoint –primary analysis | | X | |
| Primary endpoint –sensitivity analysis | | | |
| Other efficacy endpoints | | X | |
| MTT endpoints | | | X |
| Safety endpoints | X | | |
| Demographics | X | | |
| Baseline for efficacy | | X | |

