16.1.9 Documentation of statistical methods

Proprietary confidential information © 2019 Boehringer Ingelheim International GmbH or one or more of its affiliated companies

Boehringer Ingelheim

TSAP for BI Trial No: 1218.102

Page 39 of 47

Proprietary confidential information © 2019 Boehringer Ingelheim International GmbH or one or more of its affiliated companies

‘treatment-emergent’. The REP is defined as a period of 7 days after the last dose of trial medication. That means that all AEs occurring between first drug intake till last drug intake + residual effect period (REP) will be assigned to the randomised treatment. All AEs occurring before first drug intake will be assigned to ‘screening’ and all AEs occurring after the REP will be assigned to ‘post-treatment’ (for listing only). For details on the treatment definition, see [Section 6.1](#).

In general, in-text AE tables will only present AEs assigned to the randomised treatments. End-of-text tables will display in addition AEs observed ‘pre-treatment’ (including AEs observed during screening and placebo run-in regardless of treatment group) and AEs observed during post-treatment regardless of treatment group.

Analysis of other significant AEs

According to ICH E3 ([1](#)), AEs classified as ‘other significant’ needs to be reported and will include those non-serious and non-significant AEs with

- (i) ‘action taken = discontinuation’ or ‘action taken = reduced’ or
- (ii) marked haematological and other lab abnormalities or lead to significant concomitant therapy as identified by the Clinical Monitor / Investigator at a Medical Quality Review Meeting (MQRM).

AE summaries

An overall summary of AEs will be presented.

The frequency of patients with adverse events will be summarised by treatment, primary system organ class (SOC) and preferred term (PT). Separate tables will be provided for patients with other significant adverse events according to ICH E3 ([1](#)), for patients with AESI, for patients with AEs leading to discontinuation, for patients with drug-related AEs and for patients with serious adverse event (SAE). The system organ classes will be sorted alphabetically, and preferred terms will be sorted by frequency (within SOC).

The frequency of patients with AEs will also be summarised by subgroups, including age, gender, background therapy and renal function. The details of the subgroups can be found in [Table 6.4: 1](#).

Additional AE analyses

Analysis of hypoglycaemic events

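### The SAP keeps treated-but-never-randomised patients in the safety set, where its as-randomised rule cannot place them, and plans no table by drug received when a wrong kit is taken

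*SAP*

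**What the plan says.** **Assignment rule.** Protocol 7.3.4: "Safety analysis will be performed on TS, with patients assigned to the treatment they were randomised". SAP 6.1 agrees and covers efficacy and safety together: "The efficacy and safety analyses will follow the intention-to-treat (ITT) principle in assigning patients to treatment groups, i.e. patients will be analysed as randomised". SAP 7.8.1 repeats it for adverse events (AEs): "all AEs occurring between first drug intake till last drug intake + residual effect period (REP) will be assigned to the randomised treatment".

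**Wrong drug.** SAP 6.1 foresees this: "If a patient erroneously receives the wrong trial drug, the patient will be analysed" as randomised. It adds one safeguard: "Additionally, the AEs with an onset during the time of the incorrect study treatment will also be listed separately". Code C1.2 in SAP Table 6.2:1 makes taking a wrong kit at any visit an important protocol violation. It is found by comparing the kit recorded with the kit assigned, and is finally judged after database lock.

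**Safety population.** Protocol 7.3 requires TS patients to be both randomised and treated. SAP sections 4 and 6.3 drop the first condition from the TS and place it in the full analysis set (FAS). The TS now reads: "It consists of all patients treated with at least one dose of study drug. The TS is the basis for safety analyses".

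**Treated without randomisation.** Code C2.1 describes the case: "Patient treated according to eCRF but not randomised by IVRS". It removes the patient from the FAS and the randomised set (RS). The TS is not mentioned. Code C1.1, in the same table, does name the TS when it excludes a randomised patient who took no drug.

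**The concern.** The SAP widened the safety set but left unchanged the assignment rule that depends on it. A C2.1 patient belongs to the TS, yet has no randomised treatment under which to be tabulated. SAP section 7 expresses percentages relative to the treatment group, and the hypoglycaemia model in SAP 7.8.1 needs a treatment value. In the public text, no section says which column this patient enters. Even the table of important violations, planned by treatment group on the TS, has no place for a C2.1 case.

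For wrong-kit patients there is a rule, but it answers a different question from the one a safety reader asks. Safety tables are read as what happened on linagliptin and what happened on placebo. Data collected on the other drug pull the arms together on average, and for safety that is not the cautious direction. For a rare event of special interest, one patient can decide which column shows the case.

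**Working it through.** **1. Can the rules be applied together?**

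| Case | In TS? | Arm under SAP 6.1 / 7.8.1 |
|---|---|---|
| Randomised, no drug taken (C1.1) | No, removed explicitly | Not needed |
| Randomised, wrong kit (C1.2) | Yes | Randomised arm |
| Treated, never randomised (C2.1) | Yes, not removed | None exists |

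Because C1.1 names the TS and C2.1 does not, and the TS definition itself dropped randomisation, C2.1 patients stay in the safety set. The third row has no solution under the stated rule.

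**2. What does the 6.1 listing cover?** It lists AEs with onset during incorrect treatment. Events of special interest and investigator-defined hypoglycaemic AEs are AEs, so they appear there. It does not cover laboratory values, unless the investigator reported the change as an AE. It also omits asymptomatic hypoglycaemia that was not reported as an AE, although SAP 7.8.1 tabulates that. Exposure is summarised per treatment in SAP 7.7 with no separate rule. No incidence table changes, and C2.1 patients are not covered.

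**3. Denominator.** Protocol 7.7 needs 100 per arm and expects about 2.2% dropout: 100 / (1 − 0.022) = 102.2, rounded up to 103 per arm, 206 in total. This reproduces the plan.

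**4. One patient, whole trial, one event seen in nobody else.** Suppose the patient was randomised to placebo but took linagliptin throughout.
- By drug received: linagliptin 1/104 = 0.96%, placebo 0/102 = 0%.
- As randomised: linagliptin 0/103 = 0%, placebo 1/103 = 0.97%.
- Each arm moves by about 1 point and the difference by 0.96 + 0.97 = 1.93 points. A 1 versus 0 count is tabulated as 0 versus 1.

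**5. Common events.** Assume k patients in each arm took the other drug throughout. The as-randomised risk difference is then the true one times (1 − 2k/103). Assume also AE rates of 30% and 20%.

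| k per arm | Factor | 10-point difference shown as |
|---|---|---|
| 1 | 0.981 | 9.8 |
| 3 | 0.942 | 9.4 |
| 5 | 0.903 | 9.0 |

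**6. Patients with no arm.** With u C2.1 patients beyond the 206, the share of the TS without an arm is u/(206 + u): 1/207 = 0.5% for u = 1 and 3/209 = 1.4% for u = 3.

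**7. Partial exposure.** Protocol 4.1.4 has five dispensing occasions, and the visit intervals are 4, 4, 4, 6 and 6 weeks. One wrong interval is 4/24 = 17% to 6/24 = 25% of planned treatment. Steps 4 and 5 are therefore upper cases for such a patient, except when the event falls within the wrong interval.

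The values of k and u and the AE rates are assumptions. The documents give none of them.

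**The case against.** The strongest defence is that as-randomised safety was chosen in advance and stated the same way in protocol 7.3.4, SAP 6.1 and SAP 7.8.1. It preserves the randomised comparison and gives every randomised patient exactly one arm and one denominator. The wrong-drug case is named, listed and recorded as an important violation. Safety is descriptive, so no test depends on these tables. Kits are allocated by interactive response technology, so errors may never occur. Protocol 7.5 also provides for exceptional cases to be settled before unblinding.

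Most of this stands. A reader might infer that as-randomised safety is itself an error, or that the SAP departs from the protocol on it; the documents support neither. A reader might also infer that all events of a wrong-kit patient sit under a drug not taken. That holds only for the interval of incorrect treatment, which can be one of five.

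Two things are left. The consistency argument covers randomised patients and does nothing for C2.1 patients, whom the SAP foresees and keeps. The protocol 7.5 clause allows a solution but does not state one. And the listing makes AEs visible without showing what the tables would be by drug received.

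**Conclusion.** There is a real but minor gap, cheap to close. The TS definition, code C2.1 and the as-randomised rule cannot all be applied to a treated-but-never-randomised patient. For wrong-kit patients, the plan follows a legitimate pre-specified rule but lacks a supplementary view by drug received.

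The size depends on errors whose number is not given and may be zero. One patient with an event, misassigned for the whole trial, moves each arm by about 1 percentage point. Common AE contrasts barely change: a 10-point difference shows as 9.8 with one full swap per arm. The effect matters mainly for rare events of special interest. The primary analysis, sample size and power are untouched.

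It would go too far to conclude that AEs in this trial are credited to the wrong arm; the documents do not show that any such patient exists. Nor does the wider TS make sense only if all safety data move to the drug received. Restoring the randomisation condition would remove the contradiction equally well.

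The conclusion rests on the public text, from which some SAP passages have been removed.

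**What to change.** - **SAP 6.3:** define the TS as at least one dose of double-blind study drug. Protocol 4.1.6 describes the placebo run-in kit under study medication, so the present term is loose, although C1.1 makes sense only if double-blind drug is meant.
- **C2.1 patients:** either restore the randomisation condition to the TS and list these patients separately, or keep them and tabulate them by the kit received.
- **SAP 6.1:** keep the as-randomised tables. If any TS patient received a drug other than the one assigned, add the AE overview and the special-interest, hypoglycaemia, laboratory and exposure tables by drug actually received, alongside them.
- **Mixed exposure:** pre-specify one arm for the denominator, for example the drug taken for most of the exposure. List events by the drug in use at onset, and flag those within 7 days after a switch, since the plan's residual effect period is 7 days.
- **SAP section 4:** record the change.

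The cost is SAP wording and, if the condition is met, a few extra tables. The kit comparison is already planned under C1.2, so no new data are needed. The as-received tables leave the randomised comparison for the affected patients, which is why they should supplement the as-randomised tables and not replace them.
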